## 16 CONFLICT OF INTEREST

The term “conflict of interest” refers to situations in which financial or other personal considerations may compromise or have the appearance of compromising a researcher's professional judgment in conducting or reporting research. CERENOVUS will make every effort to safeguard against conflicts of interest to assure the integrity of the data, subject safety and investigator objectivity.

## Revision History

Revision Number	Revision Date (DD/MM/YYYY)	Reasons for Revision
Version 1	25JAN2022	First edition.

## 1 Study Design

This is a prospective, multi-center, single-arm, observational post market study that will consecutively enroll up to 50 subjects treated with NIMBUS at approximately 10 sites in Europe. This study will evaluate NIMBUS, post one or two unsuccessful passes of another Mechanical Thrombectomy device, in the treatment of acute ischemic stroke. Data will be collected at baseline (prior to thrombectomy), during the procedure, and post-procedure. Clinical follow up with subjects will occur over 3 months; at 24 hours and 90 days post procedure.

## 2 Treatment Assignment

This is a single arm study; all enrolled subjects will be treated with NIMBUS.

## 3 Interval Windows

Study reports will be summarized by analysis visit as defined in the protocol:

- 24 Hours post-procedure ( $\pm 8$  hours)
- 90-day follow-up ( $\pm 14$  days)

The study schedule is to be adhered to as closely as possible for all subjects. Measurements outside the interval windows will be treated as missing. In the case of repeated measurements taken at the same visit, the most recent non-missing measurement will be used unless specified otherwise.

## 4 Levels of Significance

No hypothesis tests are planned in the study. All confidence intervals will be reported at a two-sided 95% confidence level. These confidence intervals will not be used for statistical inferences, but for clinical reference purpose and are intended to convey precision in the estimates.

## 5 Analysis Sets

The following analysis sets are defined in the study:

- **Modified Intent-to-Treat (mITT) Analysis Set**

The mITT Analysis Set consists of all subjects who are enrolled into the study, and who have attempted at least one pass with the NIMBUS device (which includes deployment and retrieval with the NIMBUS device).

A subject is considered enrolled in this study after the physician confirms the subject meets all eligibility criteria, and the subject is consented.

- **mRS Analysis Set**

The mRS Analysis Set consists of all mITT subjects who meet the study criteria as defined in protocol section 9.5.

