## SCHEMATIC OF STUDY DESIGN

Assessments and imaging performed for the study are part of standard of care (SOC) for stroke treatment, and screening can occur without obtaining consent. Informed consent is mandatory and must be obtained before any data is captured in the electronic Case Report Form (eCRF).

**Footnote 1:** Optional

**Footnote 2:** Mechanical Thrombectomy

**Note 1.** All thrombectomy subjects for whom a second pass with any thrombectomy device was completed will be recorded in the site screening log.

**Note 2.** Informed Consent may be obtained at any point from imaging confirmation of an Acute Ischemic Stroke through to 7 days post-procedure.

Figure 1: Schematic of Study Design

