## SCHEDULE OF ASSESSMENTS

Table 1: Schedule of Assessments

Table Legend: X = Required; O = Optional, to be collected if performed during standard of care	Enrollment			Follow-up	
	Baseline	Procedure	Post-procedure 24hrs (+/- 8 hrs)	90 Day Follow-up (+/- 14 days)	Unscheduled 
Assessments					
ICF	X				
Eligibility Screening	X				
Demographics and Medical History	X				
IV t-PA administration	O				
Imaging 	X	X	X		O
NIH Stroke Scale (NIHSS)	X		X	O	O
Modified Rankin Scale (mRS)	X			X	O
Angiography 		X			
Review of Applicable Adverse Events (AE)		X	X	X	X
Clot Collection 		X			

(1) CT/MR Imaging and angiography will be sent to independent Imaging Core Lab for review.

(2) Due to the emergent nature of AIS, consent may be obtained after the procedure but up to 7 days post-procedure as permitted by the local regulations and EC.

(3) Per pass clot collection to be sent to Central Lab for processing.

(4) If more than one NIHSS was performed during this time period, select the worst (highest) value.

(5) To be evaluated by a qualified evaluator; pre-stroke mRS should reflect the subject's condition just prior to the stroke onset. For example, if the subject was hospitalized during stroke onset, the subject's reason for hospitalization should be taken into account when evaluating the subject's pre-stroke mRS.

(6) Assessments should be completed for unscheduled visits from the time of Discharge up to (but not including) the 90-day Follow-up, where imaging, NIHSS, or mRS is performed as part of stroke management care for the subject.

(7) The 90 day mRS must be performed by a qualified independent evaluator who is not part of the interventional treating team.

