#### 4.1 Inclusion Criteria

Prior to entry in this study, patients must meet **ALL** of the following criteria:

1. Age  $\geq$  18.
2. The subject or the subject's legally authorized representative has signed and dated an Informed Consent Form.
3. Patient has had one or two passes of another mechanical thrombectomy device without achieving mTICI 2b or better and continues to have angiographic confirmation of a Large Vessel Occlusion (LVO) in the same vessel.
4. mRS 0-1 prior to this stroke.
5. NIMBUS is used on the second or third overall pass to attempt revascularization.

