### **6.1 Screening**

Subjects presenting with AIS to the enrolling medical treatment facility will be evaluated and treated by the physician according to the institutional practice prior to enrolment in the study. A subject can be consented to participate in this study from the point of imaging confirming a large vessel occlusion up to 7 days post-procedure. Subjects will be screened against the study inclusion/exclusion criteria to determine their initial eligibility. The final eligibility criterion is the requirement for a second pass of a mechanical thrombectomy device during the index procedure, therefore, the screening log should be completed post procedurally for all AIS patients in whom a second mechanical thrombectomy pass was completed. All subjects screened will be documented on the Screening/Enrolment log, including the reason for non-participation for subjects who do not enroll.

All assessments and imaging performed for this study are part of SOC for stroke treatment. Informed consent is mandatory and must be obtained before any data is captured in the eCRF.

During the eligibility screening, the investigator will perform an initial evaluation of potential study subjects for study eligibility according to inclusion / exclusion criteria. For subjects who meet the eligibility criteria and agree to participate, informed consent will be obtained. The investigator, or designee, will explain the research study to the subject and/or the legally authorized representative and answer any questions that may arise. The possible risks and possible benefits of participation will be discussed. The subject and/or the legally authorized representative will be asked to read, review and sign the EC approved informed consent form. The informed consent process is detailed further in Section 10.3.

**A subject is considered enrolled in this study after the physician confirms the subject meets all eligibility criteria, and the subject is consented.**

All subjects *who provide written informed consent* will be entered into eCRF regardless of whether or not they participate in the study.

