### 7.3 Time Period and Frequency for Adverse Event Assessment and Follow-up

AEs shall be assessed and documented for all enrolled eligible subjects from the start of the procedure or time of consent, whichever is earlier, to the end of the study participation or until their withdrawal, whichever occurs first. AEs will not be collected by the Sponsor until after consent is obtained from the subject and/or the legally authorized representative. AEs that occur during this study should be treated by established standards of care which will protect the life and safety of the subject. Events will be followed for outcome information until resolution, stabilization or the subject exits the study, whichever occurs first. Each investigator shall provide source documentation as requested by the Sponsor to facilitate reporting and adjudication of these events.

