## **10.3 Informed Consent and Data Release Form Process**

### **10.3.1 Consent and Other Informational Documents Provided to Participants**

Subject's informed consent must be obtained and documented in accordance with specific provisions of the associated ECs, the current applicable version of ISO 14155, the ethical principles that have their origin in the Declaration of Helsinki, and that are consistent with Good Clinical Practice (GCP), and the applicable national and regional regulatory requirements. Due to the emergent nature of AIS, consent may be obtained after the procedure up to 7 days post-procedure as permitted by the local regulations and EC.

The EC must review and approve an informed consent form (ICF) specific to this study. CERENOVUS will provide each study center with an example ICF. The clinical center, to meet specific EC requirements, may modify this example ICF. Each investigational site will provide CERENOVUS with a copy of the EC approved ICF and renewed approvals and consents as appropriate for the duration of the study. The original, signed and dated ICF should be retained by the investigational site for monitoring, and a signed copy provided to the subject.

If applicable per local regional requirements, a data release form must be obtained prior to releasing subject information. The EC must review and approve the data release form specific to this study and the written data release form must be signed and dated by the subject prior to participation in this study. The original, signed and dated data release form should be retained by the investigational site for monitoring, and a copy provided to the subject.

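### Both analysis sets require consent, which may come up to 7 days post-procedure; a NIMBUS-treated patient who dies unconsented is missing from 90-day mortality, mRS and sICH, and no planned output counts such deaths

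*SAP*

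**What the plan says.** **Who is analysed.** SAP section 5 limits mITT to enrolled subjects with at least one NIMBUS pass and adds: "A subject is considered enrolled in this study after the physician confirms the subject meets all eligibility criteria, and the subject is consented". Protocol 6.1 defines enrolment the same way. The mRS Analysis Set is a subset of mITT (SAP section 5, Protocol 9.5), so it carries the same condition.

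**When consent may be given.** Note 2 to the Schematic of Study Design states: "Informed Consent may be obtained at any point from imaging confirmation of an Acute Ischemic Stroke through to 7 days post-procedure". Protocol 10.3.1 says that "consent may be obtained after the procedure up to 7 days post-procedure as permitted by the local regulations and EC", and footnote 2 to the Schedule of Assessments says the same. A legally authorized representative may sign (Protocol 4.1, item 2).

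**What is collected before consent.** Protocol 6.1: "Informed consent is mandatory and must be obtained before any data is captured in the eCRF". Protocol 7.3: "AEs will not be collected by the Sponsor until after consent is obtained from the subject and/or the legally authorized representative".

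**Where the sets are used.** Under SAP 7.5, mortality and mRS 2 or less are analysed in both sets and sICH in mITT. Deaths are scored 6 on the mRS (SAP 7.5.2, item 7).

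**What is logged.** Protocol 6.1 asks that "the screening log should be completed post procedurally for all AIS patients in whom a second mechanical thrombectomy pass was completed", with the reason for non-participation of those who do not enrol. Inclusion criterion 5 is that "NIMBUS is used on the second or third overall pass to attempt revascularization", so eligible NIMBUS-treated patients should fall within the log's scope.

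**What is reported.** Disposition covers consented subjects (Protocol 9.7.2) or consented subjects and the analysis sets (SAP 7.2). SAP 7.8 contains sensitivity analyses for mRS only.

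**The concern.** Entry to the analysis can depend on an event that happens after treatment, during days when death is possible. If nobody has signed when a treated patient dies, the plan gives that patient no route into the data. Two secondary endpoints are directly exposed. Mortality loses a death, and mRS 2 or less loses a subject who would have been scored 6. A third, sICH, may lose a bleed.

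The safeguards in the plan act only inside the sets. These are the score of 6 for deaths, the carried-forward mRS analysis, and the separate count of deaths in hospital, which SAP 7.5.3 places among the mITT ancillary analyses. Protocol 6.7 likewise keeps a deceased subject's records only if consent remains in place. Protocol 9.9 names selection bias and promises every effort to consent consecutive eligible subjects, but no output shows whether that succeeded. A reader of the report could not tell zero such deaths from several, and the results are meant to inform further studies.

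**Working it through.** **The plan's own figure.** The only design calculation is the primary endpoint margin: 1.96 × √(0.86 × 0.14 / 45) = 10.14%, stated as 10.1%. It reproduces and is not in dispute. It measures sampling precision and says nothing about selection.

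**Inputs for the illustration.**
- N = 50 in mITT (SAP section 6); N = 45 is the plan's number after 10% attrition.
- F, the reported 90-day mortality: 12% and 22%, near the 12% to 22.7% range in Protocol 1.2.2.
- P, the reported proportion with mRS 2 or less: 52%, near the top of the 38% to 53% range in Protocol 1.2.1.
- k (treated, eligible, died before consent), m (treated, eligible, not consented for other reasons) and 4 sICH cases in 50 are assumptions. The documents give none of them.

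**Mortality, deaths added, m = 0.** Adding k deaths to numerator and denominator gives 1 − (1 − F) × N/(N + k). This equals the Kaplan-Meier result with those deaths included, if nobody is censored before the last of them.

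| N | Reported F | k = 1 | k = 2 |
|---|---|---|---|
| 50 | 12.0% (6/50) | 13.7% (7/51) | 15.4% (8/52) |
| 50 | 22.0% (11/50) | 23.5% (12/51) | 25.0% (13/52) |
| 45 | 12.0% | 13.9% | 15.7% |

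At k = 1 the shift is 1.7, 1.5 and 1.9 points in the three rows. It depends on N and F and has no fixed ceiling. If k = 0, every shift is zero.

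**mRS 2 or less in mITT, m = 0.** The formula is P × N/(N + k). From 26/50 = 52.0%: 26/51 = 51.0% at k = 1 and 26/52 = 50.0% at k = 2.

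**sICH, m = 0, k = 1.** From 4/50 = 8.0%: 5/51 = 9.8% if the omitted patient had sICH, 4/51 = 7.8% if not. The sign depends on a fact the study does not hold.

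**What the living non-consenters can do.** Take 6/50, k = 1 and m = 20, with mortality q among the 20. Mortality over all treated eligible patients is (7 + 20q)/71. This equals 12% when q = (0.12 × 71 − 7)/20 = 7.6%. Below that, the reported 12% is too high; with q = 0 the full figure is 7/71 = 9.9%. For mRS, (26 + 20r)/71 equals 52% when r = (0.52 × 71 − 26)/20 = 54.6%. Above that, the reported 52% is too low. The direction is therefore fixed only for the omitted deaths taken alone.

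**The case against.** The strongest reply has five parts.

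- **Consent may be in place in time.** A representative may sign, and the window opens at imaging confirmation. The documents are silent on consent after death and leave timing to local regulations and the ethics committee. This stands: the loss is possible, not certain, and k may be zero.
- **The log already captures these patients.** Largely true, and it makes the remedy cheap. But neither document tabulates the log. It must give a reason for non-participation; it need not record NIMBUS use, verified eligibility or vital status. Protocol 12.1.8 lists it in the site file only where applicable.
- **These are secondary, descriptive endpoints with wide intervals.** At 6/50 the exact 95% interval is 4.5% to 24.3%, much wider than a shift of 1.5 to 1.9 points per death. That limits the weight of the point. It does not answer it, because the interval conveys precision and not who was left out.
- **The overall bias may run either way.** Correct. A reader might infer that the consent rule flatters the device overall. The documents do not support that: the outcomes of living non-consenters are unknown, and plausible values reverse the sign.
- **A count of zero would not be conclusive.** Also correct. A reader might infer that one reported count closes the matter, but a zero could reflect an incomplete log. Its completeness has to be stated with it.

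**Conclusion.** The point holds as a gap in the analysis sets and in reporting. By the plan's own definitions, a treated, otherwise eligible patient who dies with no consent obtained is outside mortality, mRS and sICH, and the report as planned would show no sign of it. Taken alone, each such omission lowers estimated mortality and leaves mRS 2 or less the same or too high; sICH could move either way.

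The size is modest and conditional: about 1.5 to 1.9 mortality points for one death, at N of 45 to 50 and reported mortality of 12% to 22%, with no living non-consenters counted. It rests on an assumed k, and on local rules for consent after death that the documents do not describe. It warrants a small addition to the plan and does not call the study's main result into question.

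**What to change.** 1. **SAP 7.2.** Add one aggregate disposition row from the screening log, as local rules permit: otherwise eligible NIMBUS-treated patients not enrolled, split into k who died before consent and m not consented for other reasons. Query the site where the log does not show NIMBUS use, eligibility or vital status. State how complete the log is.
2. **SAP 7.8.** If k is above zero, add one mortality figure, 1 − (1 − F) × N/(N + k), with F the mITT Kaplan-Meier rate and N the mITT size. Add the matching mITT figure for mRS 2 or less, P × N/(N + k), with the k deaths scored 6. Label both as correcting for pre-consent deaths only. State that the m patients have unknown outcome, and that subjects with missing mRS are treated like observed ones.
3. **sICH and mRS Analysis Set results.** State k beside each and leave both uncorrected. The bleeding status of the omitted patients is not collected, and membership of the mRS set needs baseline data that unconsented patients do not have in the eCRF.

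**Cost.** One table row, two short calculations and two notes, with no eCRF data on unconsented patients. Some site queries would be retrospective: SAP Version 1 is dated 25 January 2022, after the planned study end of Q2 2021. The sensitivity figures will be slightly less favourable if k is above zero, and eligibility of unconsented patients will rest on the log and the sites' answers.

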## 6 Sample Size Justification

There is no hypothesis test for this post-market study, approximately 50 treated subjects are deemed sufficient to evaluate the performance of NIMBUS.

Approximately 50 subjects will be consecutively enrolled using commercially available Mechanical Thrombectomy devices during the preceding one or two passes. With an enrolled sample size of up to 50 and an attrition rate of no more than 10%, the precision (margin of error) for the primary endpoint is anticipated to be around 10.1% based on 2-sided 95% confidence intervals, where the primary endpoint rate is estimated to be 86%.

$$\text{Margin of error} \approx 1.96 \times SE$$

$$= 1.96 \times \sqrt{\frac{p(1-p)}{n}} = 1.96 \times \sqrt{\frac{0.86 \times (1-0.86)}{45}} = 10.1\%$$

where  $SE$  denotes the standard error and  $p$  denotes the proportion of subjects who achieve the primary endpoint.

## 7 Analyses to be Conducted

### 7.1 General Conventions

Descriptive summary statistics will be presented for all endpoints. The number and percentage of subjects will be summarized for categorical variables. Unless specified otherwise, percentages will be based on subjects with non-missing values. Descriptive statistics for continuous variables will include the number of subjects, mean, standard deviation, median, first quartile (Q1), third quartile (Q3), minimum and maximum. All statistical analyses will be performed using SAS® Studio, Version 9.4 or later.

#### 1. Baseline

Unless specified otherwise, the last non-missing measurement collected during the baseline visit is considered as the baseline measurement (prior to the start of the index procedure).

- The pre-stroke mRS score will be considered as the baseline mRS score.
- The highest (worst) NIHSS score will be considered as the baseline NIHSS score should a subject have more than one non-missing NIHSS score at baseline.

#### 2. Stroke onset date and time

Pre-stroke events are defined as those events that happened prior to the stroke onset date and time.

- For witnessed stroke, the stroke onset date and time as reported from the case report form (CRF) will be used;
- For un-witnessed stroke, the date and time when the patient was last seen well from the CRF will be used.

### **3. Study Day**

Unless specified otherwise, study day will be calculated as the difference between the assessment date and index procedure date, i.e., assessment date – index procedure date, and the date of index procedure is considered as Day 0.

#### **7.2 Disposition of Study Subjects**

The number and percentage of subjects in each analysis set will be provided, together with a summary of number of subjects who completed or discontinued the study with associated reasons.

Enrollment by site will be summarized for all consented subjects and each analysis set as well.

#### **7.3 Demographic and Baseline Characteristics**

All demographic and baseline characteristics will be summarized for each analysis population, including but are not limited to the following:

- Demographics and baseline characteristics
- Medical history
- Baseline stroke characteristics
- Baseline mRS, NIHSS scores

#### **7.4 Procedural Characteristics**

Procedural characteristics and procedure per pass data will be summarized descriptively for each analysis set for the passes Nimbus was used in addition to all procedure passes. Data are including but are not limited to the following:

- Type of mechanical thrombectomy device used
- Type of catheter applied overall and at per pass level, e.g., balloon guide catheter, intermediate catheter, microcatheter etc.
- Clot retrieval per pass
- mTICI scores at the end of procedure and after each pass

#### **7.5 Primary and Secondary Endpoint Analyses**

mTICI scores and embolization to a new territory (ENT) will be summarized using the assessments from the independent core lab. Unless instructed otherwise, missing values will be excluded from the analysis. Exact CIs will be conducted around the percentage, unless instructed otherwise.

All-cause mortality and mRS  $\leq 2$  at 90 days will be analyzed using mITT and mRS analysis sets, all other endpoints will be analyzed using the mITT analysis set.

#### 7.5.1 Primary Endpoint Analysis

- **Successful Revascularization (mTICI  $\geq 2b$ ) with NIMBUS as determined by an Independent Core Lab.**

The primary endpoint is successful revascularization after the final pass of NIMBUS, where the successful revascularization is defined as an mTICI score of 2b or greater.

The number and percentage of subjects with a procedural mTICI score  $\geq 2b$  following the final pass of NIMBUS will be summarized, excluding mTICI scores from other devices applied after the final pass with NIMBUS.

Subjects with a missing mTICI score (from the imaging core lab) for the final pass using Nimbus, will be imputed with the final (end of procedure) mTICI score from the imaging core lab if the final pass using Nimbus is the last procedural pass, there were no post mechanical thrombectomy interventions and no intra-arterial thrombolytic agent performed after the final Nimbus pass.

